10.2.2 Adverse Event Overview

An overview of AEs will be presented consisting of the number and percentage of subjects experiencing at least one event for each of the following AE categories:

- Any TEAE
- Any TEAE related to study drug according to the investigator
- Any severe TEAE (Grade 3 and above according to National Cancer Institute (NCI) Common Terminology Criteria for Adverse Events (CTCAE) version 4.03)
- Any serious TEAE (SAE)
- Any treatment-emergent SAE related to study drug according to the investigator
- Any TEAE leading to discontinuation of study drug
- TEAEs of Special Interest
- Any TEAE leading to death
- Any deaths
- Deaths occurring \leq 30 days after last dose of study drug
- Deaths occurring $>$ 30 days after last dose of study drug.

The overview of AEs per 100 patient-years of exposure will also be provided for the above categories.

10.2.3 Treatment-Emergent Adverse Events by SOC and/or PT

TEAEs will be summarized by SOC and PT; by maximum relationship to study drug as assessed by the investigator (e.g., reasonable possibility or no reasonable possibility) and SOC and PT; by maximum severity and SOC and PT; and by subject number and SOC and PT. Specific adverse events will be counted once for each subject for calculating percentages, unless stated otherwise. In addition, if the same adverse event occurs multiple times within a subject, the highest severity and level of relationship to investigational product will be reported.

In addition, TEAEs will be summarized by PT and sorted by decreasing frequency for upadacitinib 30 mg group for Safety_1 Population, and by the total active group for ALL_UPA Population.

10.2.4 Treatment-Emergent Adverse Events per Patient-Years of Exposure

Exposure-adjusted AEs per 100 patient-years will be provided by SOC and PT, where AEs per 100 patient-years of exposure are defined as the number of AEs divided by the total exposure in 100 patient-years. The study drug exposure is defined as (last dose – first dose) + 1.

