Congenital Anomaly An anomaly detected at or after birth, or any anomaly that results in

fetal loss.

Persistent or Significant Disability/Incapacity

An event that results in a condition that substantially interferes with the activities of daily living of a study subject. Disability is not intended to include experiences of relatively minor medical significance such as headache, nausea, vomiting, diarrhea, influenza, and accidental trauma (e.g., sprained ankle).

Important Medical Event
Requiring Medical or Surgical
Intervention to Prevent
Serious Outcome

An important medical event that may not be immediately lifethreatening or result in death or hospitalization, but based on medical judgment may jeopardize the subject and may require medical or surgical intervention to prevent any of the outcomes listed above (i.e., death of subject, life threatening, hospitalization, prolongation of hospitalization, congenital anomaly, or persistent or significant disability/incapacity). Additionally, any elective or spontaneous abortion or stillbirth is considered an important medical event. Examples of such events include allergic bronchospasm requiring intensive treatment in an emergency room or at home, blood dyscrasias or convulsions that do not result in inpatient hospitalization, or the development of drug dependency or drug abuse.

All AEs reported from the time of study drug administration until 30 days after discontinuation of study drug administration will be collected, whether solicited or spontaneously reported by the subject. In addition, study procedure-related serious and nonserious AEs will be collected from the time the subject signs the study-specific informed consent.

AbbVie will be responsible for Suspected Unexpected Serious Adverse Reactions reporting for the Investigational Medicinal Product in accordance with global and local requirements.

Adverse events will be monitored throughout the study to identify any of special interest that may indicate a trend or risk to subjects.

Adverse Events of Special Interest

The following AEs of special interest will be monitored during the study:

- Serious infections
- Opportunistic infections
- Herpes zoster
- Active TB
- Malignancy (all types)
- Adjudicated gastrointestinal perforations
- Anemia
- Neutropenia
- Lymphopenia
- Renal dysfunction
- Hepatic disorder
- Adjudicated cardiovascular events (e.g., major adverse cardiovascular event [MACE])

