10.0 Safety Analyses

10.1 General Considerations

Safety data will be summarized for each safety population. Safety summaries will be presented by treatment group. For ALL_UPA Population, upadacitinib 30 mg, 15 mg and a total group for all subjects on upadacitinib will be summarized. For the safety analysis, subjects are assigned to a treatment group based on the treatment actually received, regardless of the treatment randomized.

A subject's actual treatment sequence will be determined by the most frequent dose regimen received in Period 1.

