10.2.1 Treatment-Emergent Adverse Events

For Period 1, treatment-emergent adverse events (TEAEs) are defined as any adverse events that begin or worsen in severity after initiation of study drug through 30 days following the last dose of study drug in Period 1 or first dose in Period 2, whichever is

earlier. For Period 2, TEAEs are defined as any adverse events that begin or worsen in severity after initiation of study drug through 30 days following the last dose of study drug in Period 2. Events where the onset date is the same as the study drug start date are assumed to be treatment-emergent. All TEAEs will be summarized overall, as well as by primary MedDRA SOC and PT. The SOCs will be presented in alphabetical order, and the PTs will be presented in alphabetical order within each SOC.

The number and percentage of subjects experiencing TEAEs will be summarized.

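### Rates per 100 patient-years count adverse events to 30 days after the last dose but divide by first-to-last-dose time only, so events after the last dose overstate them, modestly and by different amounts in different groups

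*SAP*

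**What the plan says.** **Event window (SAP 10.2.1).** For Period 1, treatment-emergent events run "through 30 days following the last dose of study drug in Period 1 or first dose in Period 2, whichever is" the earlier. For Period 2 they run "through 30 days following the last dose of study drug in Period 2". The data will exist, since Protocol 6.1 states: "All AEs reported from the time of study drug administration until 30 days after discontinuation of study drug administration will be collected". The Operations Manual (2.2 and 4.1) adds a follow-up contact about 30 days after the last dose, and continued event collection in subjects who stop drug but stay in the study.

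**Denominator (SAP 10.2.4).** The rule is "AEs per 100 patient-years of exposure are defined as the number of AEs divided by the total exposure in 100 patient-years", and "The study drug exposure is defined as (last dose – first dose) + 1". No other section adds the 30 days to this time or restricts the rate numerator to events starting on drug.

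**Where the rates are used.** SAP 10.2.4 applies them to all treatment-emergent events by system organ class and preferred term, SAP 10.2.5 to serious events and events leading to discontinuation, and SAP 10.2.6 to each event of special interest. For the overview in SAP 10.2.2, "The overview of AEs per 100 patient-years of exposure will also be provided for the above categories". Those categories include deaths more than 30 days after the last dose.

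**Groups shown.** SAP 10.1: "For ALL_UPA Population, upadacitinib 30 mg, 15 mg and a total group for all subjects on upadacitinib will be summarized".

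**The concern.** An event rate per unit of person-time needs events and time from the same window. Here the 30 days after the last dose can add events but never time. The relative error is larger when on-drug time is short, so it differs between groups with different exposure or early stopping. Two groups with the same underlying event rate could then show different rates, and part of any real difference would be discontinuation pattern or planned treatment length rather than drug effect.

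Deaths more than 30 days after the last dose show the mismatch most plainly. They lie wholly outside the denominator, yet the overview asks for them per 100 patient-years of exposure.

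**Working it through.** The documents give no adverse event rate, expected event count or stopping rate, so there is no planned figure to reproduce. The check asks how far the SAP rate departs from the rate of events starting between first and last dose.

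**Inputs from the documents**
- Planned treatment (Protocol Synopsis): 30 mg, 48 weeks = 336 days; 15 mg, 36 weeks = 252 days; Period 1, 12 weeks = 84 days.
- Tail after the last dose: 30 days, cut at the first Period 2 dose for Period 1 tables.

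**Assumptions**
- k, the off-drug event rate divided by the on-drug rate: 1, with 0.5 and 0 as alternatives.
- Early stopping in Period 1: 5% or 20% of a group, at Day 28.
- Subjects who continue go straight into Period 2, so their Period 1 tail is zero.
- Everyone else is followed for the full 30 days. Shorter follow-up would reduce the effect.
- For 15 mg, exposure starts at the first upadacitinib dose.

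**Formula.** With on-drug rate r, on-drug days E and tail days T, the expected number of events is proportional to rE + krT. Dividing by E gives r(1 + kT/E), so the overstatement factor is F = 1 + kT/E.

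**Period 1.** With a fraction f stopping at Day 28, E per subject is 84(1 − f) + 28f and T per subject is 30f.

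| f | E (days) | T (days) | F, k = 1 | F, k = 0.5 |
|---|---|---|---|---|
| 0% | 84.0 | 0 | 1.000 | 1.000 |
| 5% | 81.2 | 1.5 | 1.018 | 1.009 |
| 20% | 72.8 | 6.0 | 1.082 | 1.041 |

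If one arm had 20% stopping and the other 5%, the ratio of their rates would be off by 1.082/1.018 = 1.063, about 6%.

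**ALL_UPA, no early stopping.** Every subject has T = 30.

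| Group | E (days) | F, k = 1 | F, k = 0.5 |
|---|---|---|---|
| 30 mg | 336 | 1 + 30/336 = 1.089 | 1.045 |
| 15 mg | 252 | 1 + 30/252 = 1.119 | 1.060 |

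The ratio of the two groups is off by 1.119/1.089 = 1.03, about 3%.

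**What drives the ALL_UPA effect.** If 20% of the 30 mg group stopped at mid-course (Day 168), mean exposure would be 0.8 × 336 + 0.2 × 168 = 302.4 days and F = 1 + 30/302.4 = 1.099. That is still below the 15 mg group with nobody stopping. The 30 mg group would need 50% stopping at mid-course (mean 252 days) to reach 1.119.

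**No off-drug events.** At k = 0, F = 1 throughout.

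**The case against.** **The effect is small against the noise.** In Period 1, 40 and 20 subjects give 40 × 84/365.25 = 9.2 and 20 × 84/365.25 = 4.6 patient-years. At an assumed 300 events per 100 patient-years that is about 28 and 14 events. Treating the counts as Poisson, the 95% interval for the rate ratio spans about a factor of exp(1.96 × √(1/27.6 + 1/13.8)) = 1.9 either way. A shift of 3% to 6% would not be visible, least of all for rare events of special interest. This stands, and it limits the importance of the point.

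**No decision rests on these rates.** The plan specifies no test on them. Percentages of subjects with events are also reported and are unaffected, and serious events, events leading to discontinuation and events of special interest are listed. The 30 mg and 15 mg groups are not a designed comparison, because the 15 mg group is the placebo arm after its Week 12 switch. This also stands.

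**The formula is stated openly and follows a convention.** True, but a numerator running 30 days past the last dose is not an on-drug count, so calling the result an on-drug rate does not remove the mismatch. Last minus first plus 1 also includes any interruption days. The SAP version history says that the exposure calculation was adjusted in version 2.0 but not how, so nothing can be inferred from it.

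**Events leading to discontinuation are little affected.** Such an event ordinarily starts before the drug is stopped for it. Adding 30 days to that denominator would lower the rate with no compensating events, by about 8% for a 30 mg completer (336/366 = 0.918) and 11% for a 15 mg completer (252/282 = 0.894). This stands, so one replacement denominator for every category would be wrong.

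**Conclusion.** The mismatch is in the current text, and its direction is certain: whenever events start after the last dose, the planned rate exceeds the on-drug rate. Its size is modest. At equal event rates on and off drug it is about 2% to 8% for a Period 1 group with 5% to 20% stopping at Day 28, and, with no early stopping, 8.9% (30 mg) and 11.9% (15 mg) in ALL_UPA. The stopping fractions and the off-drug event rate are assumptions that the documents do not settle.

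Three stronger readings are tempting but not supported.
- A reader might infer that rates could double or triple. For one subject who stops at Day 28 the factor is 1 + 30/28 = 2.07, and at Day 14 it is 1 + 30/14 = 3.14. The SAP, however, pools events over total exposure, so these single-subject ratios are never reported.
- A reader might infer that the group with more or earlier stopping is always inflated most. That describes Period 1. In ALL_UPA mean exposure decides, and the 15 mg group is inflated more even if nobody stops.
- A reader might infer that the safety conclusions are invalid. No formal test uses these rates, and the subject percentages are untouched.

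The point is worth correcting because the rates appear in the main safety tables and the correction is cheap.

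**What to change.** In SAP 10.2.4:

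- For rates of treatment-emergent events, serious events and events of special interest, define patient-years as time from first dose to the earliest of last dose + 30 days, first Period 2 dose (for Period 1 tables), death, or end of participation. Restricting the rate numerator to events starting on drug would also align the windows. The two versions agree when on-drug and off-drug rates are equal; otherwise the first averages over the 30-day tail and the second does not, so the SAP should say which is used.
- Keep last minus first plus 1 for the drug-exposure table and for the rate of events leading to discontinuation.
- In the overview (SAP 10.2.2), give deaths more than 30 days after the last dose as counts only.

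The cost is a short text change and one derived variable from dates already collected. The drawback is slightly less comparability with programs that use on-drug time, which can be met by also showing the on-drug rate.

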10.2.5 SAEs (Including Deaths) and Adverse Events Leading to Study Drug Discontinuation

SAEs (including deaths) and TEAEs leading to study drug discontinuation will be summarized by SOC and PT and in listing format.

In addition, the event rate per 100 patient-years of exposure will also be provided by SOC and PT for each treatment emergent SAE and TEAE leading to study drug discontinuation.

10.2.6 Adverse Events of Special Interest

Adverse events of special interest will be summarized by SOC and PT and will be based on standardized or company MedDRA queries (SMQs or CMQs), or based on adjudication results. Adverse events of special interest are categorized as follows:

- Serious infections
- Opportunistic infection excluding tuberculosis and herpes zoster
- Possible malignancy
- Malignancy
- Non-melanoma skin cancer (NMSC)
- Malignancy excluding NMSC
- Lymphoma
- Hepatic disorder
- Adjudicated gastrointestinal perforation
- Anemia
- Neutropenia
- Lymphopenia
- Herpes zoster
- Renal dysfunction
- Active tuberculosis
- Adjudicated MACE
- Adjudicated VTE

Detailed information about the search criteria are provided in [Appendix B](#).

Tabular listings of adverse events of special interest will be provided.

In addition, the event rate per 100 patient-years of exposure will also be provided by SOC and PT for each AESI.

10.3 Analysis of Laboratory Data

Data collected from central and local laboratories, including additional laboratory testing due to an SAE, will be used in all analyses, except for Baseline where SAE-related laboratory assessments on or before the first dose of study drug will be excluded. The clinical laboratory tests defined in the protocol operations manual (e.g., hematology and clinical chemistry) will be summarized.

Mean change from baseline to each applicable post-baseline visit will be summarized for selected laboratory variables, with the number of observations, baseline mean, and visit mean for each safety population. The change from baseline mean, standard error, and 95% confidence interval will be presented for the mean change from baseline within each treatment group and difference between treatment groups (active vs. placebo). Percent change from baseline in LDL-C, HDL-C, total cholesterol and ratio of LDL-C to HDL-C will also be summarized similarly.

Changes in laboratory parameters will be tabulated using shift tables by NCI CTC criteria (Version 4.03) for each safety population. A shift table from baseline to the worse value (based on NCI CTC criteria) during treatment will be created. A similar shift table will be provided to summarize shifts from baseline to the final post-baseline value.

Laboratory abnormalities will be evaluated based on Potentially Clinically Important (PCI) criteria ([Appendix C](#)). For each laboratory PCI criterion, the number and percentage of subjects who have at least one laboratory value meeting the criteria will be summarized for each safety population. Listings will be provided to summarize subject-level laboratory data for subjects meeting PCI criteria.

For the purpose of assessing for potential Hy's law cases, the frequencies and percentages of subjects with post baseline liver specific function test values that meet the following criteria of potential clinical interest should be presented:

- $ALT \geq 3 \times ULN$
- $ALT \geq 5 \times ULN$

- $ALT \geq 10 \times ULN$
- $ALT \geq 20 \times ULN$
- $AST \geq 3 \times ULN$
- $AST \geq 5 \times ULN$
- $AST \geq 10 \times ULN$
- $AST \geq 20 \times ULN$
- $TBL \geq 2 \times ULN$
- Alkaline phosphatase $\geq 1.5 \times ULN$
- ALT and/or $AST \geq 3 \times ULN$ and concurrent $TBL \geq 1.5 \times ULN$
- ALT and/or $AST \geq 3 \times ULN$ and concurrent $TBL \geq 2 \times ULN$

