Investigational Plan:	This is a Phase 2, multicenter, randomized, double-blinded, parallel-group, placebo-controlled study to evaluate the efficacy and safety of upadacitinib in adult subjects with moderate to severe HS. The duration of the study will be up to 57 weeks and will include an approximately 35-day screening period followed by a 48-week treatment period and a 30-day follow up visit after the last dose of study drug. Subjects who meet eligibility criteria will be randomized in a 2:1 ratio to 1 of the 2 arms as shown below: • Upadacitinib 30 mg once daily (QD) (N = 40): Daily oral doses of upadacitinib 30 mg from the Baseline visit up to the Week 12 visit (Period 1). Subjects will remain on blinded upadacitinib 30 mg through Period 2. • Placebo (N = 20): Placebo for upadacitinib from the Baseline visit up to the Week 12 visit (Period 1). At Week 12, subjects will be switched to blinded upadacitinib 15 mg QD through Period 2.
Key Eligibility Criteria:	Eligible subjects will be adult females and males who are at least 18 years of age at Screening with moderate to severe HS (defined as a total AN count of ≥ 5 at Baseline, presence of HS lesions in at least 2 distinct anatomic areas, and draining fistula count of ≤ 20 at Baseline). Subjects should have a diagnosis of HS for at least 1 year prior to baseline. Subjects must also have an inadequate response (lack of efficacy after a course of therapy) or an intolerance to oral antibiotics for treatment of HS.
Study Drug and Duration of Treatment:	Upadacitinib 30 mg QD film-coated tablets for oral administration, 48 weeks in duration. Upadacitinib 15 mg QD film-coated tablets for oral administration, 36 weeks in duration. Placebo for upadacitinib QD film-coated tablets for oral administration, 12 weeks in duration.
Date of Protocol Synopsis:	25 October 2020

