Urine pregnancy test (at Baseline and thereafter at monthly intervals)		*	✓	*	>	*	V	>	*	*	*	>
Beta-D-glucan (Japan only)	✓											

Activity	Screening	Baseline	Week 2ª	Week 4 ^a	Week 8 ^a	Week 12 ^a	Week 16 ^a	Week 24 ^a	Week 32 ^a	Week 40 ^a	Week 48 ^a / Premature Discontinuation	w Up
	Day -35 to Day -1	Day 1	Day 15	Day 29	Day 57	Day 85	Day 112	Day 168	Day 224	Day 280	Day 336	30-Day Follow Up Visit/Call
* CENTRAL LABS												
HBV/HCV screening, HIV Ab (Note: HBV testing is done every 12 weeks where required)	*											
Serum pregnancy test, FSH (as applicable)	*											
QuantiFERON-TB Gold Plus test (and/or local PPD skin test)	1											
High sensitivity C- reactive protein (hsCRP)		*	✓	*	*	*	*	*	*	✓	✓	
Clinical chemistry and hematology	✓	✓	✓	√	✓	√	√p	✓	✓	✓	*	
Urinalysis	✓	✓		✓	✓	✓	V	✓	✓	✓	✓	
Total cholesterol, high- density lipoprotein cholesterol (HDL-C), low- density lipoprotein cholesterol (LDL-C), triglycerides (fasting)		*				*		*			*	
Blood samples for PK assay		V	1		*	*	V	1				
Optional biomarker samples: Whole blood RNA		*		>		>		*			*	
Optional biomarker sample: Whole blood DNA		>				>		*				
Optional biomarker sample: Plasma/serum proteomic		1		1		*		1			*	
Optional biomarker sample: Whole blood immunoglobulin G (IgG)		>		>		>		>			*	
Optional biomarker sample: B cell subsets		1		√		*		*			√	

Activity	Screening	Baseline	Week 2ª	Week 4 ^a	Week 8 ^a	Week 12 ^a	Week 16 ^a	Week 24 ^a	Week 32 ^a	Week 40 ^a	Week 48 ^a / Premature Discontinuation	w Up
	Day -35 to Day -1	Day 1	Day 15	Day 29	Day 57	Day 85	Day 112	Day 168	Day 224	Day 280	Day 336	30-Day Follow Up Visit/Call
Optional biomarker sample: PBMC		*				*		*				
R TREATMENT												
Randomization/drug assignment		1										
Re-Randomization/drug assignment						*						
Dispense study drug & subject dosing diary		*	*	>	>	*	✓	>	*	*		

- a. Subjects will be brought back to their original visit schedule (calculated from Baseline) if they are out of the visit window, for all visits indicated.
- b. Additional clinical hematology tests are recommended at Week 20 (unscheduled visit) for subjects who have absolute neutrophil counts < $1,200/\mu$ L or hemoglobin < 9 g/dL at Week 16.

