2.2 Study Design Overview

This is a Phase 2, multicenter, randomized, double-blinded, parallel-group, placebo-controlled study to evaluate the efficacy and safety of upadacitinib in adult subjects with moderate to severe HS.

The duration of the study will be up to 57 weeks and will include an approximately 35-day screening period followed by a 48-week double-blinded treatment period and a 30-day follow up visit after the last dose of study drug.

[figure not shown]
Subjects who meet eligibility criteria will be randomized in a 2:1 ratio to 1 of the 2 arms as shown below:

- Upadacitinib 30 mg once daily (QD) (N = 40): Daily oral doses of upadacitinib 30 mg from the Baseline visit through Period 1 and Period 2.
- Placebo (N = 20): Placebo for upadacitinib from the Baseline visit up to the Week 12 visit (Period 1). At Week 12, subjects will be switched to blinded upadacitinib 15 mg QD through Period 2.

The schematic of the study is shown in [Figure 1](#). Further details regarding study procedures are included in the Operations Manual ([Appendix E](#)).

The primary efficacy analysis will be conducted when all ongoing subjects have completed their Week 12 visit.

Figure 1. Study Schematic

HiSCR = $\geq 50\%$ reduction from baseline in the total AN count, with no increase in abscess or draining fistula counts

PBO = placebo; UPA = upadacitinib

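### By-dose laboratory and vital-sign percentages in ALL_UPA rest on unequal exposure and unequal numbers of assessments, so 30 mg is expected to look worse than 15 mg even with no dose effect

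*SAP*

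**What the plan says.** SAP 10.3 (Analysis of Laboratory Data) specifies a crude any-time summary for each safety population: "For each laboratory PCI criterion, the number and percentage of subjects who have at least one laboratory value meeting the criteria will be summarized". The same section counts subjects crossing liver-test thresholds at any time after baseline and tabulates the shift from baseline to the worst on-treatment grade. SAP 10.4 applies the any-time rule to vital signs. PCI means potentially clinically important. For laboratory values, SAP Appendix C sets this at CTCAE Grade 3 or above with at least one grade of worsening from Baseline.

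SAP 10.1 fixes the columns: "For ALL_UPA Population, upadacitinib 30 mg, 15 mg and a total group for all subjects on upadacitinib will be summarized".

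The two doses are not given for the same time. The protocol synopsis lists "Upadacitinib 30 mg QD film-coated tablets for oral administration, 48 weeks in duration" and "Upadacitinib 15 mg QD film-coated tablets for oral administration, 36 weeks in duration". For the placebo arm, SAP 2.2 says: "At Week 12, subjects will be switched to blinded upadacitinib 15 mg QD through Period 2".

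For adverse events the SAP does allow for exposure. Section 10.2.2 says "The overview of AEs per 100 patient-years of exposure will also be provided for the above categories", and 10.2.4 to 10.2.6 extend such rates to SOC and PT tables, serious events, discontinuations and events of special interest. Sections 10.3 and 10.4 have no counterpart.

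**The concern.** The chance that a subject ever has a qualifying value grows with time on drug and with the number of times the subject is measured. In ALL_UPA both are larger for 30 mg. A reader who sets the two columns side by side for low neutrophils, low lymphocytes, low hemoglobin or raised transaminases may take a gap produced by the schedule for an effect of dose. The worst-value shift table has the same property, because the worst of nine values tends to be more extreme than the worst of five. Nothing in 10.3 or 10.4 adjusts for this or warns the reader.

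**Working it through.** **Exposure.** 30 mg runs from Baseline to Week 48: 48 − 0 = 48 weeks. 15 mg runs from the Week 12 switch: 48 − 12 = 36 weeks. Both match the synopsis.

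**Number of assessments.** In Protocol Appendix D the row "Clinical chemistry and hematology" is marked at Screening, Baseline and Weeks 2, 4, 8, 12, 16, 24, 32, 40 and 48. The vital-signs row has the same marks.
- 30 mg: 11 marks less Screening and Baseline = 9.
- 15 mg: only Weeks 16, 24, 32, 40 and 48 follow the first 15 mg dose = 5.
- Fasting lipids are marked at Baseline and Weeks 12, 24 and 48, which gives 3 for 30 mg and 2 for 15 mg.

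Five is the natural reading of an on-upadacitinib column. The SAP does not say outright that placebo-period values are left out. Unscheduled and local values also count, so actual numbers may differ from the schedule.

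**Independent assessments, same per-assessment risk p in both columns.** P(at least one) = 1 − (1 − p)^k, with k = 9 or 5. The documents give no p, so a range is shown.

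| p | 30 mg | 15 mg | Ratio |
|---|---|---|---|
| 0.5% | 4.4% | 2.5% | 1.78 |
| 1% | 8.6% | 4.9% | 1.76 |
| 2% | 16.6% | 9.6% | 1.73 |
| 5% | 37.0% | 22.6% | 1.63 |

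For lipids (3 against 2) the ratio over the same range is 1.46 to 1.50.

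**Correlated assessments.** A beta-binomial model has a = p(1 − ρ)/ρ, b = (1 − p)(1 − ρ)/ρ and P(at least one) = 1 − B(a, b + k)/B(a, b). At p = 2%:

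| ρ | 30 mg | 15 mg | Ratio |
|---|---|---|---|
| 0.3 | 7.95% | 5.95% | 1.34 |
| 0.6 | 4.63% | 3.90% | 1.19 |
| 0.9 | 2.56% | 2.42% | 1.06 |
| 1 | 2.00% | 2.00% | 1.00 |

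**Constant hazard, ignoring how often subjects are measured.** The ratio is (1 − e^(−48h))/(1 − e^(−36h)). It is 1.33 at h = 0.001 per week and 1.30 at h = 0.005.

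**Dropout.** Equal dropout in both groups of up to 30% by 48 weeks leaves the ratio of mean draws at 1.80.

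**Chance.** With 40 and 20 subjects, independent draws and p from 1% to 5%, the 30 mg percentage comes out higher in 67% to 86% of trials with no dose effect. It is tied or lower in the rest.

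**What rates would and would not remove.** Dividing by time on drug removes the 48 against 36 week difference. Assessment density still differs: 9/48 = 0.188 per week against 5/36 = 0.139 per week, a ratio of 1.35.

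**The case against.** The strongest reply is that no dose comparison is planned. The objective is 30 mg against placebo, SAP 10.3 and 10.4 give between-group differences only for active against placebo, and ALL_UPA is a descriptive safety summary. SAP 6.0 tabulates treatment duration by group, so the unequal exposure is visible. All of this stands. The risk is that a descriptive table is misread, not that a test is invalid.

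A reader might infer that these are the only tables setting the two doses side by side for blood-count and liver risks. They are not. SAP 10.2.6 tabulates anemia, neutropenia, lymphopenia and hepatic disorder as events of special interest, by dose in ALL_UPA and with rates per 100 patient-years. Protocol 6.1 also makes a laboratory abnormality an adverse event if it meets the Section 6.2 criteria. The Table 3 limits there for hemoglobin, neutrophils, lymphocytes and white cells match the hematology cut-offs in SAP Appendix C. Many such values will therefore reach the exposure-adjusted tables. Values not confirmed on repeat may not, and the liver thresholds in SAP 10.3 do not match Table 3 one for one. By-visit mean changes and the shift to the final value do not grow with the number of assessments in this way.

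A reader might also infer that a false dose-response is built in, or that it holds for any abnormal value. Neither follows. The excess is an expectation, it vanishes under full persistence, and chance can reverse it with groups this small. PCI laboratory values are Grade 3 or above with worsening. Nothing in the documents supports a risk as high as 5% per draw on one parameter. The independent-draw ratios are therefore an upper end.

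**Conclusion.** The point holds as a limited one. In ALL_UPA the crude PCI and liver-threshold percentages, and the worst-value shifts, are expected to be less favorable for 30 mg than for 15 mg with no true dose effect. For the percentages at 9 against 5 assessments, the size is about 1.6 to 1.8 times under independence, about 1.2 to 1.3 times under moderate correlation or a constant hazard, and nil under full persistence. For total cholesterol and triglycerides (3 against 2) it is at most about 1.5 times. This rests on equal per-assessment risk in both groups, adherence to the schedule, and a 15 mg column limited to values after the first 15 mg dose.

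It does not touch the efficacy analysis or the Safety_1 comparison, where both arms share one schedule to Week 12. It is a cheap improvement that brings the value-based tables into line with what the SAP already does for adverse events.

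**What to change.** In SAP 10.3 and 10.4, for ALL_UPA:

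1. Beside each PCI and liver-threshold percentage, report the first-occurrence rate per 100 patient-years on upadacitinib.
2. State that the 15 mg column uses only values after the first 15 mg dose, and say which Baseline it uses. SAP 9.1, written for efficacy, ties Baseline to the first study drug dose, which in this arm is placebo. The PCI rule depends on this choice.
3. Footnote that the percentages and worst-value shifts are not a dose comparison because exposure and number of assessments differ, and that rates still leave a 1.35-fold difference in assessment density.
4. Optionally, add a secondary table restricted to Weeks 16, 24, 32, 40 and 48 in subjects who entered Period 2. It equalizes the scheduled number of draws (5 against 5) but not time since first dose. The 30 mg subjects have by then completed 12 weeks on drug, so early events and early dropouts are excluded for that dose only, which could make 15 mg look worse. The table must say so and should not be the main display.

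The cost is SAP wording and slightly more tabulation. Conduct, data collection and efficacy analyses do not change.
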